# **VI. STATISTICS:**

The objective of this study is to estimate change in the six functional/physical measures (described in Section VI) over time. The information gained in this study will be used for future larger studies. These measures will be collected at baseline, two weeks, 4 weeks, and 8 weeks. Other secondary endpoints, such as patients' Self Reported Improved (or PROMIS) Health Assessment Questionnaire, PROMIS Short Form v1.0 – Physical Function 12a, MDASI, FACT-Fatigue, GVHD associated measures and corticosteroid dose will also be collected over the same time course. We plan to approach 70 patients (3 patients each month for an approximate period of 24 months of accrual). We expect that about 85% (60 patients) will agree to participate in the study. Further if 10 (20%) out of 60 patients drop out early due to developing significant weakness, disease progression, or have a prolonged and complicated inpatient hospital course, we expect 50 patients to complete the 8 week measures. With 50 patients, we will have an 80% power to detect an effect size of 0.404 in a functional measure change from baseline to 8 weeks using a paired t-test with a 0.05 two-sided significance level.

To explore the possible corticosteroid dose effect on the functional measures, graphical methods will be used to present data and the cumulative steroid exposure may be correlated with functional measures over time in a repeated measures analysis when appropriate. Furthermore, 2-week or 4-week cumulative steroid exposure may be compared between 6-month non-relapse deaths and others, provided patients all survive past 2 weeks or 4 weeks.

We expect about 20% non-relapse mortality rate at 6 months (NRM6). With about 10 non-relapse deaths, we will explore potential difference in baseline and/or the change of functional/physical measures between 6-month non-relapse deaths vs others. With 10 non-relapse deaths and 40 others, we will have an 80% power to detect an effect size of 1.011 in the difference of a functional measure at baseline between two groups using a two-sample t-test with a 0.05 two-sided significance level.

We will also evaluate adherence rates to the exercise regimen and drop-out rates/patterns, which is very important for the future larger study planning.

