At the end of the study, we will summarize the pattern of the functional/physical measure change, pattern of exercise and other secondary measures, using collected information from all 50 patients. Repeated measures analysis or generalized estimating equation maybe applied to estimate the magnitude of the measure change over time. In the same model we will also evaluate the correlation between/among different measures. These models incorporate the intra-patient correlation into consideration when these measures are recorded multiple times from each patient.

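### Weakness is a listed reason for dropout, yet the plan sets no analysis population, missing-data method or death rule for the change to Day 56; read literally, it estimates decline in completers only.

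*Combined protocol and SAP*

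**What the plan says.** The primary objective (Section II) is to estimate change in six physical and functional tests after corticosteroids are started. The hypothesis in the same section expects a decline by Day 28 that may be stronger at Day 56.

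Section VI expects 60 patients to enrol and 10 to "drop out early due to developing significant weakness, disease progression, or have a prolonged and complicated inpatient hospital course". It continues: "we expect 50 patients to complete the 8 week measures". The 80% power for an effect size of 0.404 is then computed on those 50, "using a paired t-test with a 0.05 two-sided significance level".

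The closing paragraph of Section VI says the pattern of change will be summarised "using collected information from all 50 patients". On the model it says: "Repeated measures analysis or generalized estimating equation maybe applied to estimate the magnitude of the measure change over time". Drop-out rates and patterns will be evaluated, with future planning as the stated reason.

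Section V (Study Plan) keeps measuring participants who remain inpatients and follows outpatients who are admitted. It records 5x sit-to-stand only as a time in seconds.

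The documents give no missing-data assumption or method, no defined analysis set, no sensitivity analysis, and no rule for a patient who dies before Day 56. The only survival condition, in Section VI, applies to the comparison of 2- or 4-week steroid exposure.

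**The concern.** When patients leave because they have become weak, those who remain are on average the stronger ones. A paired t-test needs both visits, so it drops every patient without a Day 56 value, and Day 56 is the visit at which the plan thinks the decline may be greatest. The average decline among completers could then be smaller than that of the enrolled cohort.

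This bears directly on the study's purpose, because estimation is the primary aim and Section VI says: "The information gained in this study will be used for future larger studies". If the population is instead left open, it can be settled after the data are seen.

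The choice between the two optional models also matters. A likelihood-based repeated measures model remains valid when dropout depends on values already observed. Ordinary unweighted GEE generally needs dropout to be unrelated to outcome. The plan does not choose between them.

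**Working it through.** **1. The plan's own figure.** Inputs from Section VI: n = 50, effect size 0.404, two-sided 0.05, paired t-test. Noncentrality = 0.404 × √50 = 2.857, df = 49, critical t = 2.010. Power = 79.96%, which agrees with the stated 80%. The power arithmetic is sound; the gap is in the analysis plan.

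**2. Bias of a completers-only mean.** Assumption, not in the documents: dropouts decline k SD more than completers, with the SD of change equal to 1. With 50 completers and 10 dropouts, and c the completers' mean decline,

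cohort decline = [50c + 10(c + k)] / 60 = c + k/6.

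Completers therefore understate the decline by k/6. The standard error with 50 patients is 1/√50 = 0.141. If the cohort decline is 0.404 SD:

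| k | Understatement k/6 | Completers show | In standard errors |
|---|---|---|---|
| 0 | 0 | 0.404 | 0 |
| 0.25 | 0.042 | 0.362 | 0.3 |
| 0.5 | 0.083 | 0.321 | 0.6 |
| 1.0 | 0.167 | 0.237 | 1.2 |

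Section VI labels the 10 dropouts as 20%, but 10/60 = 16.7%. With 12 of 60 lost the understatement is 0.2k: 0.05, 0.10 and 0.20 SD for the three non-zero values of k.

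**3. Mixed reasons.** Weakness is one of three reasons and no split is given. If a third of the dropouts leave through weakness and the rest decline like completers, the understatement is k/18. That is 0.028 at k = 0.5 (0.028/0.141 = 0.2 standard errors) and 0.056 at k = 1.0 (0.4 standard errors).

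**4. What a model would recover.** Simulation under assumed values: 60 patients, mean changes of −0.10, −0.20 and −0.404 SD at Days 14, 28 and 56, correlation 0.7 between adjacent visits, 10 dropouts, 4,000 trials per case. The log-odds weight for outcome-driven dropout is 1.0 per SD of decline. The ranges cover dropout driven by the Day 28 or the Day 56 value.

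| Outcome-driven dropouts | Completers show | Model, exit after Day 28 | Model, exit after Day 14 | Model, exit before Day 14 |
|---|---|---|---|---|
| 3 of 10 | 0.36–0.37 | 0.38–0.40 | 0.37–0.39 | no gain |
| 10 of 10 | 0.24–0.29 | 0.32–0.40 | 0.28–0.34 | no gain |

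A repeat run agreed to within about 0.01 SD. The model removes the bias when dropout follows an observed value, removes part of it otherwise, and gains nothing for exits before the first follow-up visit.

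**5. What 50 means.** Section VI uses 50 for patients completing 8 weeks, then for a baseline comparison ("With 10 non-relapse deaths and 40 others"), and then for the final summary. The baseline comparison does not need an 8-week value, and it counts deaths among the 50. The three uses do not describe one defined set.

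**6. The clock for deaths.** Section III times non-relapse mortality at 6 months after enrolment; Section V times the Day 180 follow-up from transplant. Section IV sets no limit on time since transplant. Since 180 − 56 = 124, a patient who starts steroids after about post-transplant day 124 reaches study Day 56 only after the Day 180 follow-up. Survival tracked to that point does not always give vital status at study Day 56.

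**7. Sit-to-stand.** A patient too weak to finish five stands has no time in seconds, so a patient who attends can still be missing because of the outcome. The AMAT has a 0–3 sit-to-stand item, but it enters only through a summed score.

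**The case against.** The paired t-test appears only in the sample-size sentence. The paragraph on analysis offers repeated measures or GEE, both of which can use partial data, and 50 may simply be the planning number carried forward. This stands: a reader might infer that the plan commits to discarding dropouts, and the documents do not establish that. The alternative reading leaves the analysis set undefined, so the gap remains on either reading.

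Continued measurement in hospital, follow-up of admitted outpatients and review of drop-out patterns all reduce the loss. They do not say how a missing Day 56 value enters the estimate, and Section VI still lists a prolonged inpatient course as a reason for dropout.

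The larger bias figures need every dropout to behave as if lost through weakness, which the three listed reasons do not support. Patients already near the bottom of a bounded scale (manual muscle score, Brooke, AMAT) have less room to fall, so k could be small or even negative on those measures.

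A reader might also infer that a later trial would be mis-sized by a calculable amount. The documents do not support that: Section I foresees interventional studies, which would not normally be sized on a one-arm paired decline. Nor can deaths by Day 56 be projected reliably, since Section VI gives only a non-relapse rate of about 20% at 6 months, without relapse deaths or timing.

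The sit-to-stand point is smaller and affects one test of six; the other scales can register very low values.

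**Conclusion.** The point holds as a gap in the analysis plan that should be fixed. Weakness is a stated reason for dropout, the only firmly named test of change rests on completers, and nothing says how missing values or deaths are treated. Whether the final estimate would be biased is not established. The likely direction is an understated decline, on the assumption that those who leave through weakness decline more than those who stay. The size is k/6 SD with k unknown and is zero at k = 0. In the mixed-reason case it is about 0.03 to 0.06 SD, or 0.2 to 0.4 standard errors: modest, but avoidable at little cost. The 0.17 SD figure is an upper illustration and should not be read as an expectation.

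**What to change.** 1. In the closing paragraph of Section VI, replace the reference to 50 patients with all enrolled patients who have a baseline value. Make a likelihood-based repeated measures model, using every observed Day 14, 28 and 56 value, the main estimate of change with a 95% CI. Use an ordinal model or a descriptive summary for the 1–6 Brooke scale. Keep the completers' paired t-test as supplementary.
2. State that the model removes bias only if dropout depends on observed values, and that it gains little for exits before Day 14. Add one simple sensitivity analysis that worsens dropouts' missing Day 56 values over a stated range, for example 0 to 1.0 SD.
3. Report Day 56 change among patients alive then, averaging the model's Day 56 values over those patients only. Report deaths from any cause before study Day 56 separately, and list dropouts by reason and last visit. Record vital status at study Day 56, because the Day 180 follow-up is timed from transplant.
4. For 5x sit-to-stand, record inability because of weakness and report the proportion unable at each visit.

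Cost: wording in Section VI, a little more analysis, a model assumption that must be stated, vital status noted at study Day 56, and one field on the test form. No extra patients or visits.

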## **VII. PROTOCOL MONITORING AND SAFETY**

Trained research staff will be performing study assessments and monitoring the patient carefully throughout the study period. A study physician will also be available by pager to address any concerns, distress, or questions, and will attend to the patient as needed. Regulatory monitoring will be provided by the principal investigator and the Institutional Review Board. Patient confidentiality will be ensured by use of patient initials, secure storage of clinical data, and anonymous reporting.

Health information will be protected and we will maintain the confidentiality of the data obtained from the patient's chart.

Collection of identifiers: We will collect and securely store patients' identifiers (including name and medical record number). Each patient will be assigned a study number that will be the only identifier to figure in the analytical file and personal data will not be disclosed in any form. The key linking these numbers will be retained in a securely locked file by the investigator.

Data Storage: Protection of electronic and paper records will be guaranteed. All electronic records will be stored on password-protected institution computers behind the institution firewall. Any paper records will be classified and stored in locked files inside a locked office.

Training of personnel: Only MDACC personnel trained in maintaining confidentiality, the principle investigators, co-investigators, and research staff will have access to study records.

Data sharing: Study data will not be shared with any individuals or entities. The data will be kept by the principle investigator in a locked file cabinet.

Final disposition of study records: These data will be used only for this research study. Data files will be destroyed within 5 years after publication of the findings.

